5.1.7.1. Primary Safety Endpoints

Incidence rate ratio estimates and 2-sided 95% confidence interval will be computed using Generalized Estimating Equations with a log-linked Poisson model via the PROC GENMOD procedure if there are events in the placebo group. The model will specify the use of a Poisson probability distribution with an offset= log (patient-observation period days) and model terms for treatment-as-received and each randomization strata. The 95% confidence interval for the

estimates of the difference in incidence rates will be computed using the same model. If there is no event in the placebo group, incidence rate ratio will not be calculated and confidence intervals for the incidence rate difference will be computed using Wald method. The incidence rate estimates for each arm, the estimates of the incidence rate ratio and incidence rate difference between fasinumab and placebo will be provided with the corresponding 95% confidence interval.

AE and SAE incidence will be summarized by treatment group based on the SAF-LTS by treatment group and combined fasinumab group.

Continuous variables will be summarized by baseline and change from baseline to each scheduled assessment time with descriptive statistics based on the SAF-LTS by treatment group and combined fasinumab group.

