### 9.5.3. Safety Analysis

The incidence rate is defined as the number of events divided by the duration of the overall observation period. The incidence rate will be summarized by treatment group along with 2-sided 95% confidence interval. The incidence rate differences and ratios between each fasinumab dose group and placebo will be computed and presented along with 2-sided 95% confidence intervals.

Change from baseline in joint space width of the index knee or hip will be summarized by treatment group. Time to event endpoints, such as time to JR decision, will be analyzed using the Kaplan-Meier approach.

For safety variables, the following observation periods are defined:

- The pretreatment period is defined as the time from signing the ICF to before the first dose of study drug
- The on-treatment period is defined as the day of the first dose of study drug to 4 weeks after the day of the last dose of SC study drug.
- The follow-up period is defined as from the end of the on-treatment period up to 24 weeks post the last dose of study drug (week 72).

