4.5.1. Primary Safety Variables

The primary safety endpoint in the study is safety monitoring including AE incidence, SAE, incidence, AESI incidence, changes in safety lab analyses, and incidence of anti-fasimumab antibody formation from baseline to week 52 (treatment period 1 and 2) and to week 72 (end of follow-up period).

More specifically, this includes:

- Incidence of adjudicated arthropathy events
- Incidence of destructive arthropathy events
- Incidence of JR (All JRs and AESI JRs) events – including endpoint for all JRs by the telephone survey approximately 52 weeks after the last dose of study drug
- Incidence of peripheral neurosensory AESI events

- Incidence of sympathetic nervous system dysfunction AESI events
- AE incidence, SAE incidence, changes from baseline in safety laboratory analyses, and incidence of anti-fasimumab antibody formation
- Change from baseline in minimum joint space width of the index joint (knee, hip)
- Incidence of confirmed orthostatic hypotension from baseline

The raw incidence rate is defined as the number of events divided by the duration of the observation period and presented as number of events per 100 patient-years.

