5.1.6.3. Length of Study Observation

The length of the observation period (days) will be calculated as:

- $(\text{Date of last study visit [up to End of Follow-up Clinic Visit]} - \text{date of first study drug dose}) + 1.$

The length of the total study observation period (days) will be calculated as:

- $(\text{Date of last study visit [up to End of Study Phone call]} - \text{date of first study drug dose}) + 1.$

The observation duration will be summarized for each treatment group using the number of patients (n), mean, standard deviation, median, Q1, Q3, minimum, and maximum.

The number (%) of patients with observation periods will be presented by specific time periods. The time periods of interest are specified as: ≥ 1 day, ≥ 29 days, ≥ 57 days, ≥ 85 days, ≥ 113 days, ≥ 141 days, ≥ 169 days, ≥ 197 days, ≥ 225 days, ≥ 253 days, ≥ 281 days, ≥ 309 days, ≥ 337 days, ≥ 365 days, ≥ 393 days, ≥ 421 days, ≥ 505 days, ≥ 701 days

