5.1.7. Analysis of Safety Data

The analysis of safety and tolerability will be performed on the SAF-LTS, as defined in Section 3.2.

The safety analysis will be based on the reported AEs and other safety information (clinical laboratory evaluations, vital signs, 12-lead ECG, Physical Examination, etc.).

Treatment-Emergent Potential Clinically Significant Values (PCSV) in laboratory variables, vital signs and ECG are defined in [Appendix 11.2](#).

Period of observation: The observation period will be divided into three segments: pre-treatment, on-treatment and post-treatment.

- The pre-treatment period is defined as the time between when the patients give informed consent and the start of study drug.
- The LTS on-treatment period is defined as the time from first dose of study drug up to 28 days after the last dose of study drug. The LTS post-treatment period is defined as the time starting 29 days after last dose of study drug (after the on-treatment period) to up to 24 weeks post the last dose of study drug (up to week 72).

Day 1 is the first day of study drug, Day -1 is the day before Day 1, and there is no Day 0.

The time interval to detect any on-treatment event or abnormality is between the first dose of double-blind study drug injection and the end of treatment plus 28 days. Data collected outside this interval will be excluded from the estimation of descriptive statistics and identification of abnormalities for laboratory evaluations, ECGs and vital signs. All post-baseline data during the interval will be using in the PCSV analysis including scheduled and unscheduled assessments.

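### The joint replacement (JR) rate that includes the week 100 phone survey is divided by person-time ending at week 72, so read literally it is about 39% too high for patients with complete follow-up

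*SAP*

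**What the plan says.** SAP 5.1.7.1 estimates rate ratios and rate differences for the primary safety endpoints from a log-link Poisson model fitted by generalized estimating equations. On person-time it says: "The model will specify the use of a Poisson probability distribution with an offset= log (patient-observation period days". SAP 4.5.1 uses the same term for the unadjusted rate, given per 100 patient-years: "The raw incidence rate is defined as the number of events divided by the duration of the observation period". Protocol 9.5.3 also has a single denominator: "The incidence rate is defined as the number of events divided by the duration of the overall observation period".

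SAP 5.1.6.3 defines two lengths, both starting at first dose:
- The observation period runs to the "Date of last study visit [up to End of Follow-up Clinic Visit", which is week 72.
- A second length follows: "The length of the total study observation period (days) will be calculated as". It runs to the "Date of last study visit [up to End of Study Phone call", which is week 100. No rate or offset anywhere in the SAP refers to it.

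SAP 5.1.7 uses the shorter term in a third way: "The observation period will be divided into three segments: pre-treatment, on-treatment and post-treatment". The on-treatment segment ends 28 days after the last dose, and the post-treatment segment ends by week 72.

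The events cover several windows. SAP 4.5.1 sets the primary safety endpoint to week 52 and to week 72. It then lists JR incidence, "including endpoint for all JRs by the telephone survey approximately 52 weeks after the last dose of study drug". SAP section 7 analyses the survey JRs at the final lock, after the week 72 lock.

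**The concern.** A rate needs events and person-time from the same window. Protocol 6.2.9 and 6.3.4.9 say that the phone contact asks about replacements since the last in-clinic follow-up visit. For a patient on schedule, the survey therefore adds events from the very interval that the defined observation period leaves out. A programmer who applies the defined term would count JRs to week 100 and divide by time to week 72.

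The outputs at stake are the absolute JR rate per 100 patient-years and its difference from placebo. Both are planned, and both feed a benefit-risk judgement. Protocol 1.1 names time to total joint replacement among the imbalances behind the recommendation to stop 3 mg Q4W and 6 mg Q8W.

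**Working it through.** The documents print no rate or person-time total that depends on the offset, so there is no planned figure to reproduce. The check is a comparison of period lengths.

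**Inputs.** The last dose is at week 48 (Protocol 3.1). In SAP study days (week w = day 7w + 1), week 52 is day 365, week 72 is day 505 and week 100 is day 701. Days 365 and 505 are the targets in SAP 6.4; 505 and 701 both appear in SAP 5.1.6.3.

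**Formula.** For a fixed number of events, printed rate / matched rate = matched person-time / person-time used.

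**1. All JRs to week 100 over week 72 person-time, complete follow-up.**
701/505 = 1.388, so the rate is 38.8% too high. If the factor is the same in both arms, the rate difference is multiplied by 1.388 as well. As an illustration, take an assumed 40 JRs in 1000 completers:
- Week 72 person-time: 40 / (1000 × 505/365.25) × 100 = 2.89 per 100 patient-years.
- Week 100 person-time: 40 / (1000 × 701/365.25) × 100 = 2.08 per 100 patient-years.

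**2. Some week 72 completers not reached at week 100.**
If a share q is reached, the excess is q × (701 − 505)/505 = q × 0.388. The shares are assumed.
- q = 0.9: 35%
- q = 0.8: 31%
- q = 0.5: 19%

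**3. Early last dose.**
Suppose clinic follow-up ends 24 weeks, and the phone call comes 52 weeks, after the patient's own last dose.
- Last dose at week 16 (assumed): (7 × 68 + 1)/(7 × 40 + 1) = 477/281 = 1.70.
- Last dose at week 24 (assumed): (7 × 76 + 1)/(7 × 48 + 1) = 533/337 = 1.58.

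**4. Effect on the rate ratio.**
The ratio is multiplied by the quotient of the two arms' factors. Equal factors cancel. In the extreme case of one arm stopping at week 16 and the other at week 48, it shifts by 1.698/1.388 = 1.22.

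**5. Events to week 52 over week 72 person-time, completers.**
365/505 = 0.723, so the rate would be 27.7% too low. This arises only if such a rate is run on this offset.

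**6. Events to week 72 over week 72 person-time.**
505/505 = 1, so there is no error.

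**The case against.** The strongest reply is that the offset is under-specified rather than wrong. The sentence in SAP 5.1.7.1 gives no end date and no cross-reference to 5.1.6.3. A period reaching the phone call is already defined, and section 7 keeps the survey analysis apart from the week 72 analysis. An analyst could well pair the two sensibly. It is true that no sentence says one week 72 offset serves every horizon. But the term used for the offset is the one that 5.1.6.3 ends at week 72, and nothing links the longer period to a rate. The literal instruction therefore produces the mismatch for the survey-inclusive JR rate.

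A reader might go further and infer that all JR rates are 39% too high and all week 52 rates 28% too low. The documents do not support that:
- JRs counted at the week 72 lock match week 72 person-time. So do AESI JRs, because adverse events are collected only to the end of follow-up (Protocol 7.4.1, SAP 4.5).
- Time to JR decision is analysed by Kaplan-Meier and Cox (SAP 5.1.8), and SAP 4.5.10 also lists the number and percentage of patients with JR. Neither uses the offset.
- Adverse event summaries are counts and percentages (SAP 5.1.8.1), and AESI differences also get exact binomial intervals (SAP 5.1.8.2). No sentence requires a Poisson rate to week 52 on week 72 person-time.
- The on-treatment period reaches week 52 for a patient dosed through week 48. It ends sooner for early stoppers, who are asked to keep attending (Protocol 5.3.2), so it is not a general substitute for time to week 52.

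**Conclusion.** The plan is wrong as written on a narrow point: the all-JR rate that includes the phone survey, and its difference from placebo. For patients with complete follow-up, both are about 39% too high. That figure assumes that the defined term is applied literally, that the survey endpoint is analysed as a rate by the 5.1.7.1 method, and that visits fall on schedule. It is not a trial-wide estimate: incomplete week 100 contact lowers it and early last doses raise it. The rate ratio is roughly safe when the ratio of the two periods is similar across arms, and not otherwise.

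The 28% understatement to week 52 is conditional on the same offset being used for such rates, which the SAP neither states nor rules out.

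**What to change.** In SAP 5.1.7.1, and in the rate definition in 4.5.1, match the offset to the event window:
- All-JR rate including the phone survey: the total study observation period already defined in 5.1.6.3.
- Rates to week 72: the observation period, stated to start at first dose, since 5.1.7 also gives it a pre-treatment segment.
- Any rate to week 52: time from first dose to week 52, or to last contact if earlier. If events are restricted to on-treatment events, use the on-treatment period instead.

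The cost is a few lines of SAP text and up to two further derived person-time variables for the rates. No new data are needed, and the change can be made before database lock.

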There have been several modifications to the dosing regimens for the study. Patients initially randomized to the 6 mg or 9 mg Q4W dosing regimen or matching placebo under the original protocol and amendments 1 and 2 were discontinued from study medication on 30December 2016 per US FDA request. The patients were encouraged to otherwise continue all protocol visits and complete all study procedures with the exception of receiving study medication. Under amendments 3 and 4, main study patients were randomized to 6 mg Q8W or matching placebo. Under amendment 5 global (Issued 16March 2017) or later amendments, main study patients were randomized to 6 mg fasinumab Q8W, 3 mg fasinumab Q4W, 1 mg Fasinumab Q4W, or matching placebo. Efficacy sub-study patients were randomized to 6 mg fasinumab Q8W, 3 mg fasinumab Q4W, 1 mg fasinumab Q4W, 1 mg fasinumab Q8W, or matching placebo Q4W. Patients randomized to efficacy sub-study will continue in the main study on randomized treatment after participation in the efficacy sub-study. Prior to amendment 5 global all subjects participated only in the main study. Enrollment for the main study under

amendment 5 or later was paused on 3 January 2017 not due to any safety concern, but to hold enrollment of 6 mg Q8W vs placebo until further discussion with health authorities on safety database requirement. The efficacy sub-study has completed enrollment as of 7 February 2018.

The Data Monitoring Committee recommended that the 3mg Q4W and 6mg Q8W doses be discontinued due to safety concerns. A decision was made by the Sponsor to conduct an unplanned interim safety analysis of the data to corroborate these findings. Based on the IDMC recommendation and the totality of evidence to date with regards to safety, only the 1mg Q4W, 1mg Q8W doses and placebo arms would be carried forward in the study. The 3 mg Q4W and 6Mg Q8W doses were discontinued from further dosing; however, subjects have been encouraged to remain in the study and will be followed for all study visits until completion of the end of study visit in order to continue to monitor for safety and to allow complete data collection.

The Abridged Unblinded DMC Interim Report was made available to members of the study team including the study biostatistician and study medical director. This abridged DMC report included the following subject level listings:

- Listing of Serious of Adverse Events from the Case Report Form (amendment 3)

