- Listing of Serious of Adverse Events from the Case Report Form (amendment 5 sub-study)
- Listing of Deaths (amendment 3)
- Listing of Adjudication Results for Subjects with Arthropathies (amendment 3)
- Listing of Adjudication Results for Subjects with Arthropathies (amendment 5 Sub-study), Listing of Subjects with Total Joint Replacement (amendment 3)
- Listing of Subjects with Total Joint Replacement (amendment 5 Sub-study)

Restricted to subjects randomized to Placebo SC Q4W or Q8W (amendments 3 or earlier), 6 mg SC Q4W or Q8W (amendments 3 or earlier), Placebo SC Q4W (amendment 5 sub-study), 3 mg SC Q4W (amendment 5 sub-study), 6 mg SC Q8W (amendment 5 sub-study). This report did not contain any information on the 1mg Q4W and 1mg Q8W doses or their placebo arms that are being carried forward; hence there is no risk of unblinding of the blinded study team members to doses being continued. Continued monitoring of all subjects not being dosed also remains blinded to the clinical team as to treatment received.

Given the discontinuation of the 3 mg and 6 mg doses, greater exposure to the fasinumab 1 mg dose was required to increase the size of the fasinumab safety database for potentially clinically relevant doses. Therefore, under amendment 8, patients will be randomized in a 3:3:1 ratio to fasinumab 1 mg Q8W, 1 mg Q4W or placebo. This randomization ratio was chosen based on the need to enroll more patients on the 1 mg dose regimens and the need to include placebo patients for blinding purposes.

Supportive trials include data from 2 completed fasinumab phase 1 studies in healthy volunteers (R475-PN-0817 and TD-11480), as well as data from the completed fasinumab phase 2 proof-of-concept study in patients with pain due to OA of the knee (R475-PN-0901), and results from the phase 2 study in patients with osteoarthritis of the hip or knee (R475-PN-1227).

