2. INVESTIGATION PLAN

2.1. Study Design and Randomization

This is a Phase 3, randomized, double-blind, multi-dose, placebo-controlled study to evaluate the long-term safety and efficacy of fasinumab in patients with pain due to osteoarthritis of the knee or hip. Patients are randomized into either the main study or the efficacy sub-study. After the 16-week sub-study, efficacy sub-study patients continue on the randomized treatment as part of the Long-Term Safety (LTS) study in which dosing will continue through week 48. The LTS study is made up of both main study patients and efficacy sub-study patients.

There have been several modifications to the randomization scheme for both the main study and the efficacy sub-study as follows:

- Original Protocol, Amendment 1 & 2

Under the original protocol and amendments 1 and 2, main study patients were randomized to 6 mg or 9 mg Q4W or matching placebo in a 2:2:1 ratio. Efficacy sub-study patients were to be randomized to 6 mg or 9 mg Q4W or matching placebo in a 1:1:1 ratio. Patients randomized to these earlier versions of the protocol with the 6 mg or 9 mg Q4W dosing regimen or matching placebo were discontinued from study medication but encouraged to otherwise continue all protocol visits and complete all study procedures with the exception of receiving study medication. Efficacy sub-study enrollment did not start under the original protocol and amendment 1 and 2.

- Amendment 3 & 4

Under amendment 3 and 4, main study patients were randomized to 6 mg Q8W or matching placebo in a 2:1 ratio. Efficacy sub-study patients were to be randomized to 6 mg Q8W or matching placebo in a 1:1 ratio. However, there were patients enrolled into the efficacy sub-study under amendment 3 and 4.

- Amendment 5 and 6

Under amendment 5 global or later, main study patients were to be randomized to 6mg fasinumab Q8W, 3 mg fasinumab Q4W, 1 mg Fasinumab Q4W, or matching placebo Q4W in a 1:2:2:1 ratio. However, there were no patients enrolled into the main safety study under amendment 5 or amendment 6. Efficacy sub-study patients were randomized to 6 mg fasinumab Q8W, 3 mg fasinumab Q4W, 1 mg fasinumab Q4W, 1 mg fasinumab Q8W, or matching placebo Q4W in a 1:1:1:1:1 ratio. Efficacy sub-study has completed enrollment as of 7 February 2018.

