Due to the recommendation of the Independent Data Monitoring Committee, the 3mg Q4W and 6mg Q8W doses have been discontinued as described above. This SAP will apply to the amended protocol reflecting the most recent change in doses recommended by the IDMC, now including only the 1 mg Q4W and 1mg Q8W doses and placebo arms.

- Amendment 7 (urgent safety measure)

Issued on 24 May 2018, all patients previously randomized to 3 mg Q4W or 6 mg Q8W under earlier versions of the protocol will be discontinued from study drug but encouraged to otherwise complete all remaining study visits and study procedures in the follow-up period, and the end of study phone call. Anyone previously randomized to 9 mg Q4W or 6 mg Q4W (or matching placebo) before amendment 3, or randomized to 6 mg Q8W or 3 mg Q4W under amendment 3 or subsequent amendments, was discontinued from study drug and encouraged to complete all remaining study visits and study procedures in the follow up period and the end of study phone call.

- Amendment 8

Under amendment 8, patients will be enrolled into the main safety study. They will be randomized in a 3:3:1 ratio of fasinumab 1 mg Q8W, 1 mg Q4W or placebo. Patients randomized to 1 mg Q8W will receive alternating placebo injections at the monthly visits where active study medication drug will not be given to maintain the blind.

Stratification for the main study and the efficacy sub-study are as follows:

Main study stratification

- Randomization is stratified by screening K-L score (2-3, 4) and by geographic region (North America, Latin America, Europe, or Asia/Pacific/South Africa).

Efficacy sub-study stratification

- Randomization is stratified by screening K-L score (2-3, 4), geographic region (North America, Latin America, Europe, or Asia/Pacific), and by index joint.

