3.2. The Safety Analysis Set (SAF)

Efficacy sub-study

The safety analysis set for the efficacy sub-study (SAF-substudy) includes all randomized patients in the efficacy sub-study who received any study drug during the efficacy sub-study; it is based on the treatment received (as treated). Patients who receive at least one dose of fasinumab will be classified to the respective active treatment arm for the purpose of the analysis. Treatment compliance/administration and all clinical safety variables will be analyzed using the SAF-sub-study for the efficacy sub-study.

LTS study

The safety analysis set for the LTS study (SAF-LTS) includes all randomized patients in the overall study (randomized within either the efficacy sub-study or the main study) who received any study drug during the LTS study; it is based on the treatment-as-received (as treated). Patients who receive at least one dose of active fasinumab will be classified to the respective active treatment arm for the purpose of the analysis. Treatment compliance/administration and all clinical safety variables will be analyzed using the SAF for the entire study.

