5.1.8. Exploratory Safety Endpoints

Other safety endpoints in the study are:

- The proportion of patients taking rescue medication, number of days on rescue medication, and weekly average usage of rescue medication
- The percent of patients using standard-of-care analgesic medication from week 16 to week 52
- Time to JR decision
- Survey of Autonomic Symptoms Scores:
 - number of patients reporting health symptoms for each symptom/health problem assessed at each scheduled visit
 - number of symptoms reported and total symptom impact score at each scheduled visit
- Time to AA, time to DA

The exploratory safety variables comparing incidence rate of each fasinumab dose group and placebo will be analyzed using the same method as the primary safety endpoints.

The exploratory safety variables comparing change from baseline scores of each fasinumab dose group and placebo will be analyzed using the same method as the primary safety endpoints.

Time to event endpoints will be analyzed using Kaplan-Meier approach and Cox regression will be used for comparing each fasinumab dose group and placebo by obtaining hazard ratios and their confidence intervals. The Cox regression model will include the fixed categorical effects of treatment-as-received and randomization strata.

Additionally, sensitivity analysis of the primary endpoint of incidence of destructive arthropathy as well as incidence of DA and JRs will be analyzed excluding patients who used NSAID during the trial.

Rescue Medication

The percentage of patients who use rescue medication between baseline and week 16 will be summarized by the treatment group for FAS-LTS.

Number of days patients used rescue medication during the treatment period (Day1 to Week 2, Week 2 to Week 4, Week 4 to Week 8, Week 8 to Week 12, Week 12 to Week 16...) will be summarized descriptively by treatment group. Weekly average amount of rescue medication use will be summarized by treatment group.

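### The Poisson and Cox safety models have no randomisation-cohort term, so 1 mg versus placebo ratios are open to cohort confounding: modest with concurrent placebo, possibly larger if pre-amendment 5 placebo is pooled

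*SAP*

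**What the plan says.** **Models.** SAP 5.1.7.1 specifies a log-linked Poisson model with an offset for observation time and "model terms for treatment-as-received and each randomization strata". SAP 5.1.8 says of the time-to-event endpoints: "The Cox regression model will include the fixed categorical effects of treatment-as-received and randomization strata". Under SAP 2.1 the strata are K-L score and region, with index joint added for the sub-study only. Neither amendment nor cohort is a stratum or a model term.

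**Allocation by cohort (SAP 2.1; Protocol 5.1 and 5.5 for amendment 9).**

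| Cohort | Arms and ratio | Each 1 mg arm : placebo |
|---|---|---|
| Original to amendment 2 | 6 mg Q4W, 9 mg Q4W, placebo, 2:2:1 | no 1 mg arm |
| Amendments 3/4 | 6 mg Q8W, placebo, 2:1 | no 1 mg arm |
| Amendments 5/6, sub-study | five arms, equal | 1:1 |
| Amendments 8/9, main study | "They will be randomized in a 3:3:1 ratio of fasinumab 1 mg Q8W, 1 mg Q4W or placebo" | 3:1 |

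**Comparator.** SAP 2.1 limits the plan's scope, "now including only the 1 mg Q4W and 1mg Q8W doses and placebo arms", without saying which placebo arms. The long-term safety set in SAP 3.2 "includes all randomized patients in the overall study (randomized within either the efficacy sub-study or the main study) who received any study drug", with no restriction by cohort. SAP 1.1 mentions "the 1mg Q4W and 1mg Q8W doses or their placebo arms that are being carried forward".

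**The concern.** Treatment and cohort are associated by design, and nothing in either model separates them. The offset corrects for length of follow-up, not for who was enrolled, when, or under which procedures. If background rates differ by cohort, the 1 mg ratio absorbs part of that difference.

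The primary objective is descriptive. Even so, these ratios are the plan's model-based comparison with placebo for adjudicated arthropathy, joint replacement and the other safety events. Because the placebo cohorts are not named, two analysts could follow the SAP and report different ratios from the same data.

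**Working it through.** **1. The plan's own figure.** SAP Table 1 gives 0.74% to 1.30% for 1% observed incidence in 5,250 patients. The exact binomial interval for 52/5,250 is 0.74% to 1.30%, so it reproduces. It is a one-group interval. The plan gives no figure for the precision or bias of the 1 mg versus placebo ratio.

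**2. Inputs.** From the documents: 200 sub-study patients per arm (SAP 2.2) and the allocation ratios above. Assumed, because the documents do not give them: the sizes of the amendment 3/4 and 8/9 cohorts, the event rates, the rate differences between cohorts, and 1.39 patient-years per patient. Each calculation has no drug effect (true ratio 1) and compares one 1 mg dose with placebo.

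**3. Only the two cohorts that randomised 1 mg.** Let k be the amendment 8/9 size divided by 7, and r the sub-study background rate divided by the amendment 8/9 rate. The ratio without a cohort term is

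[(200r + 3k)/(200 + 3k)] / [(200r + k)/(200 + k)].

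For r = 2 and 1,143 patients, k = 163.3. The ratio is (889.9/689.9)/(563.3/363.3) = 1.290/1.550 = 0.83. The worst cases over amendment 8/9 sizes from 50 to 6,000 are:

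| Rate difference | Sub-study rate higher | Sub-study rate lower |
|---|---|---|
| 1.25-fold | 0.94 (n = 904) | 1.06 (n = 723) |
| 1.5-fold | 0.90 (n = 990) | 1.11 (n = 660) |
| 2-fold | 0.83 (n = 1,143) | 1.20 (n = 572) |

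One difference between these cohorts can be counted from the schedules: post-baseline orthostatic checks to week 72. The main study has 15 (weeks 4 to 16: 4; weeks 20 to 52: 9; weeks 60 and 72: 2). The sub-study adds weeks 1 and 2, making 17. If detection of orthostatic hypotension scaled with that count (17/15 = 1.13), the ratio for that event would be 0.97 at worst.

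**4. If pre-amendment 5 placebo is pooled.** Let P be the amendment 3/4 size divided by 3, and r the amendment 3/4 rate divided by a common later rate. The ratio is

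(P + 200 + k)/(Pr + 200 + k).

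With 1,200 amendment 3/4 and 2,100 amendment 8/9 patients, P = 400 and k = 300:

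- r = 1.25: 900/1,000 = 0.90
- r = 1.5: 900/1,100 = 0.82
- r = 2: 900/1,300 = 0.69
- r = 0.5: 900/700 = 1.29

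**5. Cost of adjustment.** Take 3 events per 100 patient-years, equal rates and 2,100 amendment 8/9 patients. Each patient then contributes 1.39 × 0.03 = 0.0417 expected events.

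- Unadjusted, concurrent placebo (1,100 versus 500 patients): √[1/(1,100 × 0.0417) + 1/(500 × 0.0417)] = 0.264.
- With a cohort term, one dose: 1/√[0.0417 × (200·200/400 + 900·300/1,200)] = 1/√(0.0417 × 325) = 0.272. With both doses in the model it is 0.269. The increase is about 2-3%.
- Unadjusted, pooled placebo with 600, 1,200 or 3,600 amendment 3/4 patients: 0.237, 0.220 or 0.189. Against 0.269 the increase is 14%, 22% or 42%.

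**The case against.** **The larger figures need a reading the text leans against.** SAP 2.1 confines the plan to the continuing doses and placebo arms, and SAP 1.1 describes those arms as carried forward. Protocol 5.1 says earlier main-study patients had completed treatment before amendment 7, and that pre-amendment 3 patients had been taken off study drug. Read literally, SAP 3.2 would also admit every 3, 6 and 9 mg patient, so it is weak evidence of an intention to pool. This stands.

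Two things keep the question open. SAP 1.1 says the unblinded report held nothing on the placebo arms of the 1 mg doses, yet it lists amendment 5 sub-study placebo in that report. Also, the 1,750 planned placebo patients in SAP 2.2 exceed the largest possible concurrent number, 200 + 6,000/7 = 1,057. A reader might infer from this that pooling was planned. The documents do not support that: 1,750 is a whole-study planning total, set beside 5,250 patients on all fasinumab doses combined, and not a named comparator.

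**No difference in background rates is documented.** This also stands. Amendment 5 extended screening MRI to the index and contralateral joints, but joints with K-L 3 or more already required it, so a large shift in arthropathy from that source is conjecture. Making joint replacement an AESI at the same amendment leaves the count of all replacements untouched. The two 1 mg cohorts differ in calendar time, sub-study-only eligibility and the two extra orthostatic visits. None of these gives a rate ratio.

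**The shift can be small beside sampling error.** On concurrent placebo, a 1.25-fold difference moves the log ratio by at most 0.06, against a standard error of about 0.27 at 3 events per 100 patient-years. Safety carries no hypothesis test. This limits severity but does not make the comparator pre-specified.

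**A side conflict does not matter here.** SAP 2.1 says "However, there were patients enrolled into the efficacy sub-study under amendment 3 and 4", while SAP 1.1 says "Prior to amendment 5 global all subjects participated only in the main study". The two should be reconciled, but neither reading places a 1 mg arm in amendments 3/4.

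**Conclusion.** The omission of cohort and the unnamed comparator can be read directly from the SAP, and confidence in both is high. Confidence does not extend to the size or direction of bias, which are unknown; with equal background rates there is none.

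With concurrent placebo the effect is modest: at worst 0.94-1.06 at a 1.25-fold rate difference and 0.83-1.20 at two-fold. With pooled older placebo it could be larger, 0.82 at 1.5-fold under the assumed sizes. A reader might conclude that the planned ratios are biased, or that 0.82 is an expected value. Neither follows, because both need a rate difference the documents do not report and the second also needs pooling.

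The point is minor if only concurrent placebo is intended, and should be fixed if pooling is.

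**What to change.** 1. In SAP 3.2 and 5.1.7, reconcile the scope statement in 2.1 with the safety set. State that the 1 mg versus placebo models use the amendment 5/6 sub-study and the amendment 8/9 main study, each with its concurrent placebo.
2. Add a two-level cohort factor to the Poisson model and use cohort as a stratum in the Cox model. Take index joint from baseline data for all patients, since it was a randomisation stratum only in the sub-study.
3. Label any analysis that adds pre-amendment 5 placebo as a descriptive sensitivity analysis.

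The cost is SAP wording and one extra term per model; cohort follows from the amendment and the part of the study under which each patient was randomised. The standard error of the log ratio rises about 2-3% against unadjusted concurrent placebo. Against pooled placebo it rises about 14-42% under the assumed sizes, but that extra precision depends on equal rates across cohorts. This point does not call for a separate rule for sparse events.
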